5.1. Disposition

Patient disposition will be summarised by treatment group for the ITT set, unless otherwise specified.

The number and percentage of patients in each analysis set defined in Section 4.3 will be tabulated. The number and percentage of patients entered each scheduled visit will also be tabulated.

Patients who completed the study, patients who discontinued from the study and reasons of discontinuation will be tabulated using the frequency counts and percentages.

The reasons for patients not completing the study will be recorded on eCRF with the following categories: Adverse Event, Death, Lack of Efficacy, Lost to Follow-up, Non-Compliance with Study Drug, Physician Decision, Pregnancy, Progressive Disease, Protocol Violation, Recovery, Trial Screen Failure, Study Terminated by Sponsor, Technical Problem, Withdrawal by Subject, and Other.

Patient enrollment data and reasons for screen failure will be presented in a listing. Patient disposition data, including reasons for study discontinuation, will also be provided in a listing.

5.2. Protocol Deviations

The investigator or designee must document and explain in the patient's source documentation any deviation from the approved protocol. The investigator may implement a deviation from, or a change of, the protocol to eliminate an immediate hazard to study patients without prior approval of the Institutional Review Board/Ethics Committee (IRB/IEC). As soon as possible after such an occurrence, the implemented deviation or change, the reasons for it, and any proposed protocol amendments should be submitted to the IRB/IEC for review and approval, to the sponsor for agreement, and to the regulatory authorities, if required.

A deviation from the protocol is an unintended or unanticipated departure from the procedures or processes approved by the sponsor and the IRB/IEC and agreed to by the investigator. A significant deviation occurs when there is nonadherence to the protocol by the patient or

investigator that results in a significant, additional risk to the patient. Significant deviations can include nonadherence to inclusion or exclusion criteria, enrollment of the patient without prior sponsor approval, or nonadherence to FDA regulations or ICH GCP guidelines, and will lead to the patient being withdrawn from the study.

Protocol deviations will be documented by the clinical monitor throughout the course of monitoring visits. Principal investigators will be notified in writing by the monitor of deviations. The IRB/IEC should be notified of all protocol deviations in a timely manner.

Protocol deviations will be reviewed in a blind data review meeting before database lock and patients with relevant protocol deviation will be excluded from the PPS (defined in Section 4.3.3). A list of patients include in the PPS will be finalised and documented before database lock and the breaking of the study blind.

The number and percentage of patients with significant deviations will be summarised in a table for the ITT set. All protocol deviations will be presented in a listing.

6. Demographics and Baseline Characteristics

Patient demographics and baseline characteristics will be summarised for the ITT set. Individual by-patient listings will be provided to support the summary tables.

6.1. Demographics

The continuous variables include age (years), body weight (kg), height (cm), and body mass index (BMI) (kg/m^2), and waist circumference (cm) will be summarised using descriptive statistics. The categorical variables include gender, race and ethnicity will be summarised using frequency counts and percentages.

BMI (kg/m^2) is calculated as body weight in kg / (height in m)².

6.2. Tobacco Usage

Patient's tobacco usage data will be presented in a listing.

6.3. Female Reproductive Status

The method of birth control used for women along with fertility status will be recorded at the screening visit and will be presented in a listing.

6.4. Medical History

6.4.1. General Medical History

Medical history will be coded using Medical Dictionary for Regulatory Activities® (MedDRA) Version 20.1 or higher. The number and percentage of patients with any medical history will be summarised by system organ class (SOC) and preferred term (PT) for each treatment group.

6.4.2. Disease-Specific History

The haemodynamic parameters at screening collected from the previous RHC will be summarised using descriptive statistics for following parameters:

- pulmonary vascular resistance (PVR, mmHg)
- mean right atrial pressure (mRAP, mmHg)
- mean pulmonary arterial pressure (mPAP, mmHg)
- cardiac output (L/min)
- cardiac index (L/min/m²)
- pulmonary artery wedge pressure (PAWP, mmHg)

6.5. Inclusion and Exclusion Criteria

Patients will be assigned to study drug only if they meet all of the inclusion criteria and none of the exclusion criteria.

7. Treatments and Medications

7.1. Prior and Concomitant Medications

All concomitant medications taken by the patient during the study, from the date of signature of the informed consent will be recorded in the appropriate section of the eCRF. This will include all prescription drugs, herbal products, vitamins, minerals, and over-the-counter medications. Any changes in concomitant medications will also be recorded in the patient's eCRF.

A prior medication is defined as any medication that is ended prior to the date of first dose of study drug. A concomitant medication is defined as any medication that has a stop date that is on or after the date of first dose of study drug. Imputation for partial medication start dates and stop dates can be found in Appendix 13.4. Medications with completely missing stop dates will be classified as concomitant.

Medications reported on the Concomitant medications eCRF page will be presented in data listings for prior medications and concomitant medications. Concomitant medications will be summarised by the following subgroups:

- Intake of concomitant DOACs or NOACs being reported during V0 to V2: Yes/No;
- Intake of concomitant vitamin K antagonists being reported during V0 to V2: Yes/No.
- Intake of concomitant β -blockers being reported during V0 to V2: Yes/No

7.2. Study Treatments

The study drug will be initiated at 1 mg and the dosage can be increased by 0.5 mg at 2-week intervals based on tolerability up to a maximum dose of 2.5 mg tid. Study treatment will be classified into two groups, riociguat and placebo, regardless of the dosing scheme. Study drug accountability (dispensed and returned) and administration will be presented in a listing.

7.2.1. Extent of Exposure

Treatment duration in days is defined as the total number of days a patient is exposed to the study drug:

- Treatment Duration (day) = Date of last dose - Date of first dose + 1.

Because study drug adjustment may occur during the treatment period, the exposure to study drug will also be characterized by average daily dose, which is defined as below:

- Average Daily Dose (mg/day) = Cumulative dose (mg) / Treatment duration (day)

The cumulative dose (mg) will be defined as the sum of doses taken by patients during the treatment period.

Descriptive statistics will be provided for treatment duration (day) and average daily dose (mg/day) by treatment group for the safety set and the PPS. The number and percentage of patients will also be summarised according to the maximum dose level (mg) received at the end of up-titration period.

By-patient listing will be provided to support the summary table.

7.2.2. Treatment Compliance

Patient compliance with study drug will be assessed by the investigator and/or study personnel at Visit 2 and during a telephone call using direct questioning and tablet counts. Deviations from the prescribed treatment regimen will be recorded on the source document and the patient's eCRF.

The overall treatment compliance (%) will be evaluated by calculating the number of tablets taken by the patient divided by the number of tablets expected to be used during the treatment period and multiplied by 100.

The number of tablets taken will be calculated by subtracting the number of tablets returned from the number of tablets dispensed. The number of tablets expected will be calculated by multiplying the total number of days of planned exposure to study drug (treatment duration) by the number of tablets planned per day (3 tablets per day).

The overall treatment compliance (%) will be summarised using descriptive statistics.

A patient is considered compliant if overall treatment compliance is greater than or equal to 80%. A categorical summary of whether patients were compliant (yes/no) will be present. The number and percentage of patients in compliance category of <80%, >=80 and <=120%, and >120% will also be presented.

By-patient listing will be provided to support the summary table.

8. Efficacy Analysis

The primary analysis will use ITT set, all analyses on perioperative endpoints will use PEA set only; all analyses on postoperative endpoints will use PEA set and PPS. For other endpoints, the analysis set to be used is specified in each subsection below. By-patient listings will be provided to support the summary tables.

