5.7 Treatment Compliance

Patient compliance with study drug will be assessed by the investigator and/or study personnel at each visit using direct questioning and tablet counts. Deviations from the prescribed treatment regimen will be recorded on the source document and the patient's eCRF.

Compliance will be evaluated by calculating the number of tablets taken by the patient divided by the number of tablets expected to be used in the interval between visits.

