4.3.3. Per Protocol Set (PPS)

The PPS will consist of all ITT patients who fulfil all inclusion/exclusion criteria, have at least 80% overall dose compliance with study drug, have not taken any prohibited medication, have no significant protocol deviations, have valid PVR assessments at baseline (from patient history) and Visit 2, and undergo PEA as planned. All analyses using the PPS will group patients according to treatment actually received. A blind review of data will identify which patients will be included in the PPS.

The PPS will be used in the primary and secondary efficacy analyses as supportive analyses.

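### SAP 7.2.2 names two different denominators for compliance; under the one the SAP actually defines, early stoppers can score about 100% and can pass the 80% criterion for the supportive per-protocol set

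*SAP*

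**What the plan says.** SAP 4.3.3 requires PPS patients to "have at least 80% overall dose compliance with study drug". SAP 7.2.2 repeats the threshold: "A patient is considered compliant if overall treatment compliance is greater than or equal to 80" per cent.

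The numerator in SAP 7.2.2 is found by "subtracting the number of tablets returned from the number of tablets dispensed". It is then "divided by the number of tablets expected to be used during the treatment period and multiplied by 100". The expected number is three tablets a day times a number of days, and the days are described in the phrase "the total number of days of planned exposure to study drug (treatment duration) by the number of tablets planned per day".

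SAP 7.2.1, immediately before, holds the only definition of treatment duration: "Treatment duration in days is defined as the total number of days a patient is exposed to the study drug", with the formula "Treatment Duration (day) = Date of last dose - Date of first dose + 1". That is an observed length.

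Two other texts bear on the denominator. SAP 3.1 sets the treatment period as Day 1 to Day 90. Protocol 5.7 has tablets taken "divided by the number of tablets expected to be used in the interval between visits" and does not mention treatment duration.

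**The concern.** A compliance criterion for a per-protocol set is meant to identify patients who received most of the planned treatment. If the denominator ends at the patient's own last dose, the ratio measures only how regularly tablets were taken while the patient was still taking them. Early discontinuation then does not lower the score.

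The PPS supports the primary PVR analysis (SAP 8.1) and is used beside the PEA set for Visit 4 PVR, the composite and all-cause death (SAP 8.2.1, 8.2.2, 8.2.5). Titration starts at 1 mg and rises by 0.5 mg at 2-week intervals to at most 2.5 mg (SAP 3.4). The maximum is three steps up, so about 6 weeks, and a patient who stops at day 20 has had at most one step. If such patients are in the riociguat arm of the PPS, the estimate meant to describe adequate treatment would tend toward no difference. Two programmers could also build different PPS lists from the same sentence.

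**Working it through.** The documents give no compliance result to reproduce, so the check applies both readings to the same patients.

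**Inputs.** Three tablets a day (SAP 7.2.2); threshold 80% (SAP 4.3.3, 7.2.2); treatment period of 90 days (SAP 3.1); Visit 2 at Day 90+30 (SAP 13.1), hence a range of 90 to 120 planned days; last dose on the morning of PEA (SAP 3.1); 54 tablets per bottle (Protocol 5.4.1). Assumed unless stated: every tablet is taken up to the stop day and all unused tablets are returned.

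**Formula.** Compliance = 100 × (dispensed − returned) / (3 × denominator days).

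- Reading A, actual duration: denominator days = stop day.
- Reading B, planned exposure: denominator days = 90, with 120 as the upper end.

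| Stop day | Tablets taken | A: actual | B: 90 days (270 tablets) | B: 120 days (360 tablets) |
|---|---|---|---|---|
| 14 | 42 | 100% | 15.6% | 11.7% |
| 20 | 60 | 100% | 22.2% | 16.7% |
| 45 | 135 | 100% | 50.0% | 37.5% |
| 60 | 180 | 100% | 66.7% | 50.0% |
| 71 | 213 | 100% | 78.9% | 59.2% |
| 72 | 216 | 100% | 80.0% | 60.0% |

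**Threshold under B.** 0.80 × 270 = 216 tablets, or 72 full days. With 96 planned days it is 0.80 × 96 = 76.8 days; with 120 it is 96 days. Reading A has no such threshold.

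**What A still detects.** Gaps before the last dose. A day-30 stopper with 6 missed days scores 24/30 = 80.0%; with 7 missed days, 23/30 = 76.7%.

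**Why a flat 90 days is not the remedy.** A patient fully dosed to day 96 would score 288/270 = 106.7%, and to day 120, 360/270 = 133.3%. The planned length has to run to each patient's own planned last dose.

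**Other PPS criteria.** SAP 4.3.3 also requires eligibility, no prohibited medication, no significant deviation, valid PVR at baseline and at Visit 2 (within 7 days before PEA, SAP 8.1), PEA as planned, and blind review. None states a minimum exposure. SAP 5.2 defines a significant deviation by added risk to the patient and does not name early stopping. Protocol 3.1.1 describes study drug as an addition to surgery already scheduled, so stopping drug does not by itself cancel PEA.

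**The case against.** Four stronger inferences are tempting, and the documents support none of them.

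*That the SAP plainly uses actual duration.* It does not. SAP 7.2.2 speaks of planned exposure, of tablets planned per day, and of tablets expected over the treatment period, which SAP 3.1 sets at 90 days. Under that reading the day-20 stopper scores 22% and fails. What stands is a contradiction within one sentence, in which only the actual-dates term has a formula to program.

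*That early stoppers will enter the PPS.* Passing compliance is necessary, not sufficient. Those without PEA or without a valid Visit 2 PVR are out regardless, and the blind review may remove others for a relevant deviation. For patients who stop drug, SAP 3.1 specifies only the end-of-study safety follow-up visit; it does not say whether they have Visit 2 catheterisation. Some could qualify, but no more can be said. The blind review, for its part, has no written exposure criterion to apply.

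*That a main analysis depends on this.* SAP 4.3.3 calls the PPS analyses supportive, SAP 11 calls the set complementary, and Protocol 7 calls all analyses exploratory. SAP 7.2.1 also summarises treatment duration for the PPS with a by-patient listing, so short exposure would be visible, though not excluded.

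*That compliance above 120% should also bar a patient.* SAP 7.2.2 tabulates that category, but Protocol 7.6 and SAP 4.3.3 set only a floor. Unreturned tablets count as taken, so one unreturned bottle gives a day-30 stopper (90 + 54)/90 = 160% under reading A. A ceiling could exclude patients for poor drug return rather than overuse.

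**Conclusion.** The point holds as an ambiguity with a real consequence. SAP 7.2.2 labels planned exposure with a term that SAP 7.2.1 defines as actual exposure. If the defined term is applied, the 80% criterion cannot detect early discontinuation: complete intake up to any stop day scores 100%. Against 90 planned days, anyone stopping before day 72 would fail.

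The figures assume three tablets a day, full intake until stopping, all unused tablets returned, and a planned length of 90 to 120 days. The documents do not say how many patients will stop early and still have PEA with a valid Visit 2 PVR, so the effect on PPS membership or on any estimate cannot be sized. The primary ITT analysis does not change. The correction is worth making because it settles PPS membership before unblinding at almost no cost.

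**What to change.** Before unblinding, amend SAP 7.2.2:

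- Delete the parenthetical reference to treatment duration.
- Define tablets expected as 3 × the number of days from first dose to the planned last dose, whether or not the patient stopped early. For every PPS candidate the planned last dose falls on the day of PEA. That date is always available, because the PPS requires PEA.
- Keep actual treatment duration for the exposure summaries in SAP 7.2.1 only.

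Counting three tablets on the day of PEA overstates the expected number by two, since only the morning dose is due; on 270 tablets that is 2/270 = 0.7% and can be ignored. Leave the 80% floor as it is, with no upper limit added.

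The cost is one or two SAP sentences. The PPS may be slightly smaller than under the actual-duration reading.

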8.1. Primary Efficacy Endpoint

As defined in Section 3.2.1, the primary efficacy endpoint is percent change from baseline in PVR immediately before PEA at Visit 2. The PVR assessment from Visit 2 needs to be within 7 days prior to PEA. Assessments out of the time frame will be considered invalid and be treated as missing. In the case of patients who do not undergo PEA, the PVR at Visit 2 will be treated as missing.

The null hypothesis is that there is no difference between the treatment groups in percent change from baseline in PVR immediately before PEA at Visit 2, and the alternative is that the difference is not zero. The primary efficacy analyses will be conducted using the ITT set. Similar analysis will be repeated for the PPS as the supportive analysis.

The difference in the percent change from baseline in PVR immediately before PEA at Visit 2 between riociguat and placebo will be tested using the 2-sample Wilcoxon rank-sum test.

Analysis of covariance (ANCOVA) with baseline value as the covariate will be employed to test the null hypothesis as a supportive analysis. Residuals for percent change from baseline in PVR will be generated by using PROC GLM procedure with baseline value as the covariate. A quantile-quantile (Q-Q) plot of residuals with p-value from Shapiro-Wilk test will be presented to test the normality of the residuals.

To check the effect of missing values on the robustness of the primary analysis, the primary analysis will be repeated using the baseline observation carried forward approach for missing PVR values immediately before PEA at Visit 2.

The PVR will be measured at pre-PEA visit (Visit 2) and at the 6-month follow-up visit (Visit 4). Observed values, changes from baseline and percent change from baseline will be provided for PVR using descriptive statistics by treatment group and scheduled visit.

Boxplot will be used to present the percent change from baseline in PVR by treatment group and scheduled visit. The upper (lower) edge of the box represents the 75th (25th) percentile. A horizontal line in the box interior represents the median. Above the box a vertical line indicates the region from the 3rd quartile to the 95% percentile; below the box a vertical line indicates the region from the 1st quartile to the 5% percentile. Values outside the whiskers are displayed by a distinct marker.

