4.3.3 Replacements

A total of 88 patients will be randomly assigned in the study with a target of 80 patients completing the study with an assumption of a 10% dropout rate.

Therefore, drop out for any reason before the last follow-up visit (Visit 4) will be monitored continuously throughout the study, and patients that drop out will be replaced to make a total number of 88 randomised patients. In case of a high initial dropout rate, the DSMB and the sponsor will evaluate the reasons for drop out and decide in mutual agreement on potential extension of further randomisations.

5 Study Drugs

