- When frequency counts are presented, the percentage will be suppressed when the count is zero in order to draw attention to the non-zero counts. A row denoted “Missing” will be included in count tabulations where specified on the shells to account for dropouts and missing values. Percentages will be based on the total number of patients in the respective analysis set unless otherwise specified.
- Unless otherwise specified, statistical tests will be 2-sided and performed using a 5% significance level, leading to 95% (2 sided) confidence intervals (CIs). Modelling techniques will be used in an exploratory sense. No adjustments for multiplicity are made.
- Partial dates will be imputed based on the rules specified in Appendix 13.4.
- All laboratory data will be reported by using the International System of Units.
- Unless otherwise specified, the baseline will be defined as the last valid assessment, including assessments from the unscheduled visit, prior to the study drug administration.
- A Visit 2 assessment is considered as valid only when the assessment is completed within 7 days prior to PEA. For assessments at Visit 4, the nominal visit collected in electronic case report form (eCRF) will be used in the analysis. This rule is applicable to all endpoints derived by the visit.
- By-patient listings will be created for each eCRF module for all screened patients. Patients will be identified in the listings by patient number. If data are to be summarised by visit, the visit name collected on the eCRF page will be used.
- All analyses will be conducted using SAS® software Version 9.3 or later (SAS Institute Inc, Cary, North Carolina).

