4.1. Sample Size

A total of 88 patients, accounting for a 10% dropout rate, will be randomly assigned into riociguat or placebo groups at a ratio of 1:1 in the study. The sample size for this study is not based on the required statistical power to test any specific hypothesis but feasibility to initially assess the safety and efficacy of riociguat on preoperative pulmonary haemodynamics in patients with operable CTEPH.

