8.2.1. Pulmonary Vascular Resistance (PVR)

The difference in the percent change from baseline in PVR at Visit 4 between riociguat and placebo will be tested using the 2-sample Wilcoxon rank-sum test for the PEA set and the PPS.

PVR assessment at Visit 4 will use the nominal visit information collected in eCRF without considering the time window because PVR status is expected to be stable after PEA.

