8.3. Exploratory Efficacy Endpoints

Exploratory efficacy endpoints are defined in Section 3.2.3. No formal assessment of difference between treatment groups will be performed for any of the exploratory efficacy endpoints. The difference between treatment groups in exploratory efficacy endpoints will be estimated with 95% CIs to quantify the treatment effect.

Summary tables presenting observed values and changes from baseline for NT-proBNP measurement concentration (pg/mL), cardiac output (L/min), cardiac index (L/min/m²), mRAP (mmHg), mPAP (mmHg), and PAWP (mmHg) will be provided for each treatment group by scheduled visits using descriptive statistics. The difference in the change from baseline between treatment groups with 95% CIs will be estimated non-parametrically using Hodges-Lehmann estimation of location shift in the tables. The analyses will be based on the PEA set and the PPS.

Hospital length of stay in days and ICU length of stay in days will be summarised using descriptive statistics. The difference between treatment groups with 95% CI will be estimated non-parametrically using Hodges-Lehmann estimation of location shift in the table. The analyses will be based on the PEA set.

Time from start of ICU stay to end of mechanical ventilation (in hours) will be analysed using the Kaplan Meier method. Median and quartiles in days and associated 95% CI will be calculated using the LOGLOG transformation. All patients stayed in ICU who do not have end date of mechanical ventilation will be censored at the time of discharged from the ICU. The analyses will be based on the PEA set.

Proportion of in-hospital mortality will be summarised using the frequency counts and percentages for the PEA set. Proportion difference between treatment groups along with the Clopper-Pearson exact CI will be provided

The proportion of patients who need PAH-targeted therapy immediately after PEA to Visit 4 will be summarised using the frequency counts and percentages for the PEA set and the PPS. Proportion difference between treatment groups along with the Clopper-Pearson exact CI will be provided.

WHO functional class will be summarised by scheduled visit for each treatment group. Shift table of baseline functional class versus functional class at each postbaseline scheduled visit will be provided. The analyses will be based on the PEA set and the PPS.

9. Safety Analysis

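### The deciding PVR tests and the haemodynamic contrasts do not adjust for baseline; this costs some precision, mainly at Visit 4, where the SAP also leaves out a supportive ANCOVA that the protocol implies

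*SAP*

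**What the plan says.** **Visit 2 PVR (primary).** Under SAP Section 8.1 the difference in percent change "between riociguat and placebo will be tested using the 2-sample Wilcoxon rank-sum test". An ANCOVA of percent change with baseline PVR as covariate is listed as supportive, without conditions. Protocol 7.8.1 also names the Wilcoxon as the test, and makes the supportive ANCOVA depend on normal residuals.

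**Visit 4 PVR (secondary).** Under SAP Section 8.2.1 the difference "between riociguat and placebo will be tested using the 2-sample Wilcoxon rank-sum test for the PEA set and the PPS". No ANCOVA is listed. Protocol 7.8.2 says this endpoint follows the approach of the primary analysis, which includes the supportive ANCOVA. SAP Section 11 lists the changes from the protocol; for Visit 4 PVR it mentions only the analysis sets.

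**Haemodynamics (exploratory).** Under SAP Section 8.3 differences in change from baseline "will be estimated non-parametrically using Hodges-Lehmann estimation of location shift in the tables", with 95% intervals and no formal test.

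**Setting.** SAP Section 4 states that "statistical tests will be 2-sided and performed using a 5% significance level" and that "No adjustments for multiplicity are made". The sample size is "not based on the required statistical power to test any specific hypothesis" (SAP 4.1). Randomisation is unstratified (SAP 4.2). Protocol 7.8 leaves covariates to the SAP.

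**The concern.** Percent change is not the same as adjusting for baseline. It is an increasing function of log follow-up minus log baseline, so a rank test on it fixes the baseline slope at 1 on the log scale. If the true slope is lower, patients whose baseline was high by chance show larger falls in either arm, and that variation stays in the error term.

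The documents give reasons to expect a slope below 1. Baseline is a single catheterisation taken up to 180 days before Visit 1, possibly at a referring hospital. The PVR that serves as baseline also had to exceed 800 for entry. Before Visit 4 the patient has surgery to remove the obstruction.

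With about 40 patients per arm and a sample size set by feasibility, precision is scarce. Adjustment uses a value already held for every patient who has a change score.

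**Working it through.** **1. The plan's own figure.** There are 88 patients "randomly assigned into riociguat or placebo groups at a ratio of 1:1 in the study" (SAP 4.1), "with a target of 80 patients completing the study with an assumption of a 10% dropout rate" (Protocol 4.3.3). 80 × 1.10 = 88, and 80 / 0.90 = 88.9, so 88 is reproduced. That leaves 40 per arm. The plan has no power figure to reproduce.

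**2. Assumed inputs.** The documents give no SD and no baseline-to-follow-up correlation. Assumed here: correlation rho from 0.2 to 0.9; k = SD at follow-up / SD at baseline, from 0.75 to 1.5; PVR log-normal with CV 30% or 50% and median about 900, selected above 800. Rho is defined before selection.

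**3. Interval width for a plain change score.** Relative to ANCOVA the variance ratio is (1 + k² − 2·rho·k) / (k²(1 − rho²)), which is 2/(1 + rho) when k = 1.

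| rho | variance ratio | interval wider by | 80 completers act like |
|---|---|---|---|
| 0.3 | 1.54 | 24% | 52 |
| 0.5 | 1.33 | 15% | 60 |
| 0.7 | 1.18 | 8% | 68 |
| 0.9 | 1.05 | 3% | 76 |

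This is a parametric formula. It describes the Hodges-Lehmann contrasts only approximately. The PVR tests are assessed by simulation instead.

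**4. Visit 2 power by simulation.** 40 per arm, CV 30%, k = 1. The log effect is (1.96 + 0.84) × √(2/40) × s × √(1 − rho²), with s = √ln(1.09) = 0.294, so that log ANCOVA has nominal 80% power. At rho 0.5 this is 2.80 × 0.2236 × 0.294 × 0.866 = 0.159, a 14.7% fall.

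| rho | effect | Wilcoxon | rank ANCOVA | log ANCOVA | gain, rank ANCOVA over Wilcoxon |
|---|---|---|---|---|---|
| 0.3 | −16.1% | 67.4% | 75.6% | 78.9% | 8.2 |
| 0.5 | −14.7% | 71.2% | 75.7% | 78.6% | 4.5 |
| 0.7 | −12.3% | 73.4% | 76.3% | 78.2% | 2.9 |
| 0.9 | −7.7% | 75.7% | 76.3% | 79.2% | 0.6 |

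Between-patient log-SDs of 0.30 to 0.35 with within-patient log-SDs of 0.15 to 0.30 imply rho from 0.30²/(0.30² + 0.30²) = 0.50 to 0.35²/(0.35² + 0.15²) = 0.84. Over that range the gain is about 1 to 5 points; the 8 points need rho 0.3.

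**5. Visit 4 power by simulation.** Same method, CV 30%.

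| k | rho | Wilcoxon | rank ANCOVA | log ANCOVA |
|---|---|---|---|---|
| 0.75 | 0.2 | 55.0% | 73.7% | 78.7% |
| 0.75 | 0.5 | 61.7% | 74.7% | 77.8% |
| 1.0 | 0.2 | 65.9% | 76.8% | 79.9% |
| 1.0 | 0.5 | 69.2% | 74.8% | 78.0% |
| 1.5 | 0.2 | 73.6% | 76.0% | 78.7% |
| 1.5 | 0.5 | 76.1% | 76.5% | 78.5% |

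With CV 50% the rank ANCOVA gains, in the same order, are 16.4, 12.2, 9.8, 5.4, 3.4 and 0.5 points. With 2,000 runs per setting, the standard error of one power figure near 75% is √(0.75 × 0.25 / 2000), about 1 point.

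**6. Type I error.** With no treatment effect, all three tests rejected in 4.6% to 5.6% of runs.

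**The case against.** The strongest reply is that little changes where the trial is decided. The Visit 2 gain is a few points, and the SAP already commits to an ANCOVA with baseline as covariate on the same endpoint. In four simulated Visit 2 settings (median 900) that planned ANCOVA had 90.4, 51.9, 39.1 and 70.7% power, against 89.5, 52.4, 38.7 and 71.7% for a rank ANCOVA. The SAP will therefore report baseline-adjusted evidence of about equal efficiency, and what remains at Visit 2 is mostly which test is called primary. Protocol Section 7 describes all analyses as exploratory, so that label carries less weight than in a confirmatory trial. The Wilcoxon is valid, needs fewer modelling assumptions, and is the protocol's named test. All of this stands.

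It does not answer Visit 4, where the assumed losses are larger and the SAP has no adjusted analysis.

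A reader might infer that the unadjusted tests are biased or invalid, or that baseline is ignored altogether. The documents do not support either. Randomisation and the Wilcoxon hold the error rate, baseline forms the percent change, and a baseline-adjusted ANCOVA exists for the primary endpoint. Nor should the percentages in step 3 be read as the loss in the PVR tests: they are for plain change scores.

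**Conclusion.** The point holds as a modest loss of efficiency. The gain from a baseline-adjusted rank test is about 1 to 5 power points at Visit 2. At Visit 4 it is about 3 to 17 points over most assumed settings, falling below 1 when follow-up is much more variable than baseline (k 1.5, rho 0.5) and reaching about 19 at the other extreme (k 0.75, rho 0.2). For the exploratory contrasts no test is at stake; intervals are about 3% to 24% wider under equal variances. The direction was the same in every setting tried, but the size rests on assumed SDs, correlations and variance ratios. That surgery weakens the link with baseline is also an assumption.

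The firmest part needs no simulation: Protocol 7.8.2 implies a supportive ANCOVA for Visit 4 PVR, SAP 8.2.1 omits it, and Section 11 does not record the change. One might infer a deliberate decision to drop it. The documents show only that the two texts were not reconciled.

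**What to change.** Before unblinding:

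1. Restore a baseline-adjusted analysis of Visit 4 PVR in SAP 8.2.1, in line with Protocol 7.8.2.
2. Run the PVR ANCOVAs on log PVR with log baseline, and report the treatment ratio with its 95% CI. At Visit 2 this adds about 0.4 to 4.6 power points over the ANCOVA of raw percent change.
3. Make a baseline-adjusted rank test (Quade's rank ANCOVA) the deciding PVR test, and keep the unadjusted Wilcoxon as a check. Protocol 7.8.1 names the Wilcoxon, so record this in SAP Section 11 or by amendment.
4. Report baseline-adjusted differences with 95% CIs for cardiac index, mRAP, mPAP and PAWP.

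The cost is SAP text, a little programming, a documented departure from the protocol and a few more modelling assumptions. No patients or new data are needed. If the sponsor prefers to keep the Wilcoxon as primary, items 1, 2 and 4 still recover most of the benefit.
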